8.7.4. Regulatory Reporting Requirements for Serious Adverse Events and Anticipated Events

The sponsor assumes responsibility for appropriate reporting of AEs to the regulatory authorities. The sponsor will also report to the investigator (and the head of the investigational institute where required) all suspected unexpected serious adverse reactions (SUSARs). The investigator (or sponsor where required) must report SUSARs to the appropriate Independent Ethics Committee/Institutional Review Board (IEC/IRB) that approved the protocol unless otherwise required and documented by the IEC/IRB. A SUSAR will be reported to regulatory authorities unblinded. Participating investigators and IEC/IRB will receive a blinded SUSAR summary, unless otherwise specified.

An anticipated event is an AE that commonly occurs in the study population independent of exposure to the intervention under investigation. For the purposes of this study, the following SAEs will be considered anticipated events:

- Depression
- Mania
- Suicidal ideation/thinking/behavior
- Suicide attempt

- Bipolar disorder (bipolar I/bipolar II)
- Depression suicidal
- Overdose
- Intentional self-injury
- Anxiety
- Panic attacks
- Substance abuse
- Alcohol abuse
- Intoxication
- Aggression

These anticipated events will be periodically analyzed in aggregate by the sponsor during study conduct. The sponsor will prepare a safety report in narrative format if the aggregate analysis indicates that the anticipated event occurs more frequently in the intervention group than in the control group and the sponsor concludes there is a reasonable possibility that the study intervention under investigation caused the anticipated event.

The plan for monitoring and analyzing the anticipated events is specified in a separate Anticipated Events Safety Monitoring Plan. The assessment of causality will be made by the sponsor's unblinded safety assessment committee.

The sponsor assumes responsibility for appropriate reporting of the listed anticipated events according to the requirements of the countries in which the studies are conducted.

8.7.5. Pregnancy

All initial reports of pregnancy in female participants or partners of male participants must be reported to the sponsor by the study site personnel within 24 hours of their knowledge of the event using the appropriate pregnancy notification form. Abnormal pregnancy outcomes (e.g., spontaneous abortion, fetal death, stillbirth, congenital anomalies, ectopic pregnancy) are considered SAEs and must be reported using an SAE reporting form. Any participant who becomes pregnant during the study must be promptly withdrawn from the study and discontinue further study intervention.

Follow-up information regarding the outcome of the pregnancy and any postnatal sequelae in the infant will be required.

8.8. Pharmacokinetics

Venous blood samples will be collected for PK evaluation as indicated in SoA. Samples will be used to evaluate the plasma concentrations of JNJ-55308942 and metabolites (if required). In addition, some samples may be used to measure plasma concentrations of concomitant medications used by the participant. Participant confidentiality will be maintained.

8.8.1. Evaluations

Venous blood samples of approximately 2 mL will be collected for measurement of plasma concentrations of JNJ-55308942 as per SoA. The exact dates and times of blood sampling must be recorded in the eCRF.

8.8.2. Analytical Procedures

Pharmacokinetics

Plasma samples will be analyzed to determine concentrations of JNJ-55308942 using a validated, specific, and sensitive liquid chromatography-mass spectrometry/mass spectrometry (LC-MS/MS) method by or under the supervision of the sponsor.

If required, some plasma samples may be analyzed to document the presence of circulating metabolites using a qualified research method. In addition, plasma PK samples may be stored for future analysis of other co-administered treatments and the metabolite profile.

8.8.3. Pharmacokinetic Parameters and Evaluations

Pharmacokinetic and statistical analyses will be done by the sponsor or under the authority of the sponsor. A general description of the methods to be used to analyze the PK data is outlined below. Specific details will be provided in the PK Analysis Plan. Data will be listed for all participants with available JNJ-55308942 plasma concentrations by intervention. Participants will be excluded from the PK analysis if their data do not allow for accurate assessment of the PK (e.g., non-adherence to study intervention administration; missing PK draws; or early discontinuation from the study). All concentrations below the lowest quantifiable (BLQ) concentration or missing data will be labeled as such in the concentration data presentation. Concentrations below the BLQ concentration will be treated as zero in the summary statistics. All participants and samples excluded from the analysis will be clearly documented in the study report.

For all participants, based on the individual plasma concentration-time data, using the binned nominal sampling times, the following JNJ-55308942 concentrations will be summarized at Visits 2, 3, 4, 5, and 6.

$C_{\text{pre-dose}}$: observed plasma concentration measured before study intervention intake.

$C_{1.5h}$: observed plasma concentration at approximately 1.5 hours after study intervention intake (sampling window of ± 0.5 hours).

C_{4h} : observed plasma concentration at approximately 4 hours after study intervention intake (sampling window will be 2 to 4 hours post-dose, to allow flexibility, but with the preferred time point being 4 hours postdose).

Other PK parameters may be calculated as needed to characterize the PK of JNJ-55308942.

Population PK analysis of plasma concentration-time data of JNJ-55308942 may be performed if deemed useful using nonlinear mixed-effects modeling. If performed, details may be given in a

population PK analysis plan and the results of the population PK analysis will be presented in a separate report.

Pharmacokinetic/Pharmacodynamic Evaluations

The exposure-response between JNJ-55308942 and MADRS may be explored. The exposure-response between exposure and adverse events may also be explored. When applicable, details of this PK/PD analysis may be given in a separate analysis plan and the results will be presented in a separate report.

8.9. Genetics and Pharmacogenomics

A blood sample will be collected during screening to assess whether the participant:

- is carrier of the GoF P2RX7 mutation (must be CCI or CCI at CCCI nucleotide CCI for inclusion).
- is *not* a carrier of the CCI or CCI LoF P2RX7 mutations (must be CCI or CCI at rsCCI/nucleotide CCI; and must be CC at rsCCI/nucleotide CCI). In other words, participants will be excluded if they have the presence of two copies of the LoF C allele at rsCCI (exclude those with CC at nucleotide CCI), and/or has one or more copies of the LoF C allele at rsCCI (exclude those with CCI or CCI nucleotide CCI).

A second pharmacogenomic optional blood sample will be collected from enrolled participants on Day 1 to identify genetic factors that may influence the PK, PD, efficacy, safety, and/or tolerability of JNJ-55308942 and to identify genetic factors associated with BD. If collection on Day 1 is not feasible, it can be collected on any other visit during the double-blind treatment phase.

8.10. Biomarkers

Venous blood samples for the assessment of whole blood, serum, and plasma PD related biomarkers will be collected as indicated in the SoA during the double-blind treatment phase. Biomarker measurements may include cytokine levels, such as TNF- α , IL-1 β , IL-6, IL-10 and inflammatory markers, such as IL-6 receptor, CRP, and other exploratory markers. Samples may also be used to study markers of P2X7 and monocyte activation via IL-1 β release, shed P2X7 receptor and TREM2 ectodomains, and RNA expression of P2RX7, IL-1 β , and other genes related to immune and HPA axis activity. Treatment effects will be analyzed in patients with specific biomarker profiles using statistical modeling.

Biomarker blood samples that may be collected for the research assays measuring functional inhibition of P2X7 receptor in whole blood (TruCulture) may be collected at certain sites in the US, Canada, Spain, and Poland, and those collected for peripheral blood mononuclear cells (PBMCs) inflammatory profiles is taken in the US. The list of countries for these 2 biomarker assays may be updated if countries are added or removed throughout the study. This change will not be considered a protocol deviation.

All biomarker data obtained during this study may be included in ongoing cross-study analyses to investigate the relationship between depression severity, phenotypes, and biomarkers, or to help explain interindividual variability in clinical outcomes or safety. Biomarker assays may be added

or deleted based on scientific information or technical innovations under the condition that the total volume of blood collected will not be increased.

Stopping Analysis

Biomarker analyses are dependent upon the availability of appropriate biomarker assays and clinical response rates. Biomarker analyses may be deferred or not performed, if during or at the end of the study, it becomes clear that the analyses will not have sufficient scientific value for biomarker evaluation, or if there are not enough samples or responders to allow for adequate biomarker evaluation. In the event the study is terminated early or shows poor clinical efficacy, completion of biomarker assessments may not be performed.

8.11. Health Economics

Health Economics/Medical Resource Utilization and Health Economics parameters are not evaluated in this study.

9. STATISTICAL CONSIDERATIONS

Statistical analysis will be done by the sponsor or under the authority of the sponsor. A general description of the statistical methods to be used to analyze the efficacy and safety data is outlined below. Specific details will be provided in the statistical analysis plan (SAP).

9.1. Statistical Hypotheses

JNJ-55308942, compared to placebo, results in a significant improvement in the severity of the symptoms of depression in participants with BD in an MDE, as evaluated by change in MADRS total score from baseline at Week 6.

Hypotheses will be tested at 1-sided alpha 0.10. Multiplicity adjustment will not be carried out.

9.2. Sample Size Determination

The estimated sample size of 164 participants (82 participants per group) was determined based on the assumption of an effect size of at least 0.45 for the MADRS total score (difference in mean change from baseline at Week 6 between the JNJ-55308942 and placebo groups of 3.9 units with a standard deviation of 8.6). This is considered to be a clinically relevant difference in a population with BD types I or II. The standard deviation of 8.6 in the change in MADRS total score from baseline is a reasonable assumption based on data in a published phase 3 study of quetiapine in BD type I and type II depression ([Calabrese 2005](#)). Power is set at 90%, with a 1-sided alpha of 0.10 and a 6-week drop-out rate of 20%. The estimated number of completers to be included in the primary analysis is 132.

9.3. Populations for Analysis Sets

For purposes of analysis, the following populations are defined:

Population	Description
Enrolled	All participants who signed the ICF at screening

Randomized	All participants who were randomized in the study
Safety	All randomized participants who received at least 1 dose of study intervention
Full analysis set (FAS)	All randomized participants who received at least 1 dose of study intervention and have both the baseline and at least 1 post-baseline MADRS measurement

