7.2. Discontinuation of Study Intervention

A participant's study intervention must be discontinued if:

- Serious violation of protocol procedures after discussion with and agreement of the medical monitor
- The participant withdraws consent to receive study intervention
- The investigator or sponsor believes that for safety reasons or tolerability reasons (e.g., an SAE at least possibly related to the study intervention) it is in the best interest of the participant to discontinue study intervention
- The participant becomes pregnant
- Non-adherence to take the study medication. Non-adherence will be decided on a case-by-case basis depending on the number of missed capsules and the interval between missed doses.
- Aspartate aminotransferase (AST) and/or ALT exceeds 5x the upper limit of normal (ULN) (confirmed by repeat testing)

- AST and/or ALT exceeds 3x the ULN and total bilirubin exceeds 1.5x ULN (confirmed by repeat testing)

If a participant discontinues study intervention for any reason before the end of the double-blind treatment phase, then the early withdrawal assessments should be obtained, and scheduled assessments of study intervention should be continued.

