5.1.3. Imputation of Efficacy

Imputation for missing data will include the following methods (Table 3).

Table 3: Imputation of Missing Efficacy Data

Imputation	Text
Multiple Imputation (MI)	1) Copy Reference
method	2) Delta Adjustment.
Non-Responder	Participants with missing values will be imputed as non-responders.
Non-Remitter	Participants with missing values will be imputed as non-remitters.

Imputation of total scores will apply only to the MADRS. Imputation of the MADRS total score will be performed only when 1 item score is missing. If 2 or more items are missing, the total score will be left missing. The total score will be imputed by calculating the sum of the scores of the non-missing items and multiplying it by the ratio of the maximum possible number of items (i.e., 10) to the number of non-missing items (i.e., 9).

For all other efficacy scales where multiple items are summed to create a total score, if any item of the scale is missing on one visit, the total score for that scale at that visit will be left missing.

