5.3.2.1. Analysis Methods

5.3.2.1.1. Primary Analysis

The primary efficacy analysis will be performed utilizing the hypothetical estimand defined above. The change from baseline in MADRS total score will be compared between the JNJ-55308942 mg once daily group and the placebo group at Week 6 in a mixed-effects model for repeated measures (MMRM), with time, intervention (placebo or JNJ-55308942), BD type (I or II), country, P2RX7 GoF SNP mutation genotype (homozygous or heterozygous), concomitant medication status (no mood stabilizer or antipsychotic, a mood stabilizer alone, an antipsychotic alone, or a combination of a mood stabilizer and an antipsychotic), and time-by-intervention interaction as factors, with baseline MADRS total score as a continuous covariate. Data after treatment discontinuation will be considered missing. The within-subject covariance between visits will be estimated via an unstructured variance-covariance matrix. In case of convergence problems, alternative variance-covariance structures will be attempted in the following order, with the first structure that converges being used in the analysis: heterogeneous Toeplitz, standard Toeplitz, and first order autoregressive. Kenward-Roger approximation will be used to estimate the denominator degrees of freedom. Sandwich estimator will be used to address the potential misspecification of the covariance matrix when a structured covariance matrix is used due to the convergence problem with the unstructured covariance matrix.

The comparison of JNJ-55308942 versus placebo will be performed using the appropriate contrasts directly from the MMRM analysis. A 2-sided 80% confidence interval (CI) for the difference in least squares means will be presented over time. A 1-sided p-value will be calculated at Week 6. Least square means of change from baseline (+/- SE) will be presented graphically over time.

Descriptive statistics of the actual values and the change from baseline to each postbaseline time point will be presented for MADRS total score by intervention group.

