5.3.2.1.2. Sensitivity Analysis

The primary analysis based on MMRM is valid and produces unbiased estimates of the treatment effect if missing data are missing at random (MAR), meaning that the probability of a value being missing, conditional on the observed data in the statistical model, is random and not dependent on the unknown value of missing data point. The MAR assumption cannot be verified vs. missing not at random (MNAR) using observed data. Therefore, a sensitivity analysis using copy-reference multiple imputation will be conducted under the MNAR assumption to evaluate the robustness of efficacy results and the effect of the missing data. In addition, a tipping-point analysis will be conducted if the primary analysis results show a significantly greater improvement in the MADRS

total score at Week 6 in JNJ-55308942 compared to placebo (i.e., 1-sided p-value \leq 0.1 in favor of JNJ-55308942).

The copy reference multiple imputation approach does not assume a sustained benefit of experimental intervention for the efficacy data that is either not used or missing after the intercurrent event and uses an imputation method that is based on the control group distribution and the estimated correlations between time points in the control group. MAR is assumed for intermediate missing data (i.e., missing data between non-missing observations). MNAR is assumed for monotone missing (i.e., missing data after the participant experienced an intercurrent event) in participants in the experimental intervention group, where efficacy scores are assumed as if the participant had always been in the control group. MAR is assumed for missing data in the control group.

This method will employ the following 3 steps:

Step 1 – Multiple imputation

If there are participants with a non-monotone missing data pattern, datasets with only monotone missing data patterns will be created first by imputing the intermediate missing values using the Markov Chain Monte Carlo (MCMC) method, which assumes a multivariate normal distribution over all variables included in the imputation model. This imputation will be done by intervention group. The variables to be used in the imputation are treatment, corresponding baseline values, and values observed at all double-blind visits (Weeks 1, 2, 4, 6). 50 imputations will be performed to create 50 datasets that now have monotone missing (i.e., missing data after the participant experienced an intercurrent event) data pattern.

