The efficacy data that is either not used or missing after the intercurrent event at a given time point will be imputed using the imputation model of the control group, i.e., conditional on the data observed or imputed at previous time points relative to the mean of the model for the control group.

Step 2 – Analysis

The same MMRM analysis as described for the primary efficacy analysis will be performed for each of the adjusted fully imputed datasets.

Step 3 – Pooling

Rubin's methodology (Rubin 1987) will be applied to the MMRM results from the 50 imputed datasets to produce final inferences.

An additional sensitivity analysis using the delta adjustment multiple imputation (tipping-point) approach will be conducted if the results from the primary analysis show a significantly greater improvement in the MADRS total score at Week 6 in JNJ-55308942 compared to placebo (i.e., 1-sided p-value ≤ 0.1 in favor of JNJ-55308942). This approach imputes missing data over a range of possible scenarios for the treatment effect and finds a "tipping point" where the treatment effect in participants with missing data overturns the significant treatment effect. This method will

employ the same 3 steps as in the copy-reference multiple imputation sensitivity analysis except during the first step monotone missing data will first be imputed by MAR-based MI, and the imputed values in the experimental intervention group will be adjusted using a range of delta values to generate adjusted fully imputed datasets. The adjusted fully imputed datasets will be analyzed and combined using the same methods as Steps 2 and 3 of the copy-reference multiple imputation approach. The delta will be set in a range from 0 to Δ^* in increments of 1 as adding positive values results in higher (worse) scores. Δ^* represents the adjustments leading to the "tipping point". It is the smallest delta adjustment value at which conclusions change from favorable (i.e., statistically significant, 1-sided p-value ≤ 0.1 in favor of JNJ-55308942) to unfavorable. Between-group comparisons to placebo at Week 6 (e.g., 1-sided p-values, point estimates for intervention difference) will be displayed graphically for each considered delta, up to the "tipping point" adjustment. Clinical judgement will be applied to evaluate the plausibility of the assumptions underlying this "tipping point".

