5.4. Secondary Endpoint(s) Analysis

All secondary endpoints analysis will be based on the full analysis set.

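### Dosed participants with no post-baseline MADRS fall outside the FAS, so the non-responder, copy-reference and tipping-point analyses omit the earliest dropouts; Protocol 7.2 and 7.4 also conflict on assessments after study drug stops

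*Protocol*

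**What the plan says.** **Analysis set.** Protocol 9.3 and SAP 4 define the FAS identically: randomised, at least one dose, and participants must "have both the baseline and at least 1 post-baseline MADRS measurement". The Schedule of Activities (SoA) marks MADRS on Days 1, 8, 15, 29 and 43, with none in the Follow-up/Early Withdrawal column. SAP 5.3 puts the primary endpoint on the FAS. SAP 5.4 states: "All secondary endpoints analysis will be based on the full analysis set". No text on response, remission, copy-reference or tipping point names a wider set.

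**Rules for missing data.** SAP 5.1.3, Table 3: "Participants with missing values will be imputed as non-responders", with a matching rule for remission. Under copy-reference (SAP 5.3.2.1.2), for active-arm participants after the intercurrent event, "efficacy scores are assumed as if the participant had always been in the control group". The imputation step reads: "The efficacy data that is either not used or missing after the intercurrent event at a given time point will be imputed". The tipping-point analysis follows the same steps, except that values are first imputed under missing at random and then "the imputed values in the experimental intervention group will be adjusted using a range of delta values". It runs only if the primary result has a 1-sided p-value of 0.1 or less. For the primary MMRM, "Data after treatment discontinuation will be considered missing".

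**After study drug stops.** Protocol 7.2 asks for the early withdrawal assessments and adds that "scheduled assessments of study intervention should be continued". Protocol 7.4 lists stopping study treatment, whatever the reason and with a reference to 7.2, among the causes of automatic withdrawal from the study.

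**The concern.** Missing-as-failure imputation, copy-reference and the tipping point are there to show how far the result depends on people who drop out. As the set is defined, they skip those who drop out first. Protocol 7.4 withdraws participants for worsening depression that needs new intervention and for acute suicidal ideation, so first-week exits can be related to outcome.

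Nothing technical requires the exclusion. A participant with only a baseline score can be classed as a non-responder or non-remitter, and the imputation model already contains treatment and baseline.

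The conflict between 7.2 and 7.4 adds a second problem. For someone who stops before the first post-baseline MADRS, FAS membership can depend on which section the site follows. Sites also have no single rule on follow-up after study drug stops.

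**Working it through.** **1. The plan's own figure.** Inputs from Protocol 9.2: effect size 0.45 (3.9 points, SD 8.6), 1-sided alpha 0.10, power 90%, dropout 20%. The normal approximation gives 65 per arm, and 65/0.80 = 81.25, rounded up to 82 per arm, or 164. The exact t-test gives 66 per arm, or 132 completers. Both stated totals reproduce. Planned dropout is 164 × 0.20 ≈ 33 people, which bounds the number who could be excluded for this reason if dropout is as planned.

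**2. One participant, two outcomes.** Someone stops study drug on Day 3.
- If scheduled visits continue (7.2) and a MADRS is taken on Day 8, the participant is in the FAS. The primary analysis sets that score to missing, and copy-reference imputes from baseline.
- If the participant is withdrawn (7.4) and no later MADRS is obtained, the participant is outside the FAS and is not imputed.

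The data usable in the primary analysis are baseline only in both cases. Those who stop after a post-baseline MADRS are in the FAS either way.

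**3. Primary MMRM.** A baseline-only record contributes no change-from-baseline row, so the estimate does not move.

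**4. Size, under assumptions.** The documents give 20% dropout but not when or in which arm. Spread evenly over six weeks, 20%/6 = 3.33% per arm leave before Day 8, or 164 × 0.0333 ≈ 5.5 people. The range below covers 2% to 8%.

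*Simulation:* 3,000 trials per scenario, 82 per arm, 20% random dropout per arm, 50 imputations, Rubin pooling, delta in steps of 1. Assumed: SD of change 6.0/7.0/8.0/8.6 and effect 1.0/2.0/3.2/3.9 at Weeks 1/2/4/6, correlation 0.75 per two weeks, and Week 6 ANCOVA on completed data in place of the MMRM. The MADRS rows summarise trials with a significant primary result (2,713 to 2,747 per scenario). All dosed means randomised, dosed and with a baseline MADRS.

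| Early exits per arm | 2% | 3.3% | 5% | 8% |
|---|---|---|---|---|
| Median tipping point, FAS | 12 | 13 | 14 | 16 |
| Median tipping point, all dosed | 11 | 11 | 11 | 11 |
| Median per-trial ratio | 1.07 | 1.13 | 1.23 | 1.46 |
| FAS higher / equal / lower (% of trials) | 60.9 / 38.0 / 1.1 | 77.4 / 22.3 / 0.4 | 88.8 / 10.8 / 0.4 | 96.2 / 3.6 / 0.2 |
| Copy-reference effect, FAS | 3.46 | 3.52 | 3.54 | 3.53 |
| Copy-reference effect, all dosed | 3.39 | 3.40 | 3.36 | 3.25 |
| Significant on FAS, not on all dosed | 0.8% | 1.0% | 2.4% | 3.0% |
| Response difference, all dosed (FAS 10.0) | 9.8 | 9.7 | 9.5 | 9.2 |

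Smaller repeat simulations (400 and 500 trials) at 3.3% gave median tipping points of 13 against 12 and ratios of 1.12 and 1.14.

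*Tipping point by hand, SE held fixed:* SE = 8.6 × √(2/66) = 1.497, and the margin is 3.9 − 1.2816 × 1.497 = 1.981. All dosed: 1.981/0.20 = 9.9. FAS at 3.33%: the imputed share is (0.20 − 0.0333)/(1 − 0.0333) = 0.172, and 1.981/0.172 = 11.5. The ratio is 1.16. At 8% this shortcut gives 1.53 against the simulated 1.46, because it ignores the variance that delta adds, so the simulated values are used.

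*Copy-reference by hand, dropouts placed at the placebo mean:* all dosed 3.9 × 0.80 = 3.12. For excluded share q, the FAS effect is 3.9 × [1 − (0.20 − q)/(1 − q)]: 3.22 at 3%, 3.28 at 5%, 3.39 at 8%. The shifts of 0.10, 0.16 and 0.27 agree with the simulation.

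*Response, assuming 45% against 35% in the FAS:* the all-dosed difference is 0.45(1 − a) − 0.35(1 − b), where a and b are the early-exit shares on active and placebo. Balanced exits give the last table row. With a = 5%, b = 2% it is 8.45 points; with a = 2%, b = 5% it is 10.85 points.

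*Response with fixed counts, 41/82 against 33/82 (9.8 points on all dosed):* excluding 4 per arm gives 10.3 on the FAS. Excluding 8 active and 2 placebo gives 41/74 − 33/80 = 14.2. Excluding 2 active and 8 placebo gives 41/80 − 33/74 = 6.7.

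**The case against.** The FAS is stated openly and identically in both documents, so this is largely a design choice. The planned sensitivity analyses vary one thing, the missing-data assumption; a wider set also varies the population. The study is a proof of concept at 1-sided alpha 0.10 with no multiplicity adjustment (Protocol 4.3 and 9.1). The tipping point has no pass mark and is judged clinically, and response and remission are also reported on observed data. SAP 5.2 reports discontinuations with reasons by arm, and SAP 6.3 gives analysis-set sizes by arm, so the excluded number is nearly visible already.

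The tipping-point contrast is largely mechanical: with more active-arm records imputed, a smaller delta suffices. Values of 11 and 13 are both about three times the planned 3.9. In the 500-trial run at 3.3%, the FAS value was at least 4 while the all-dosed value was below 4 in only about 2% of significant trials. The 8% scenario places 40% of planned dropout before Day 8, for which the documents offer no support.

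All of this stands and limits the size. It does not explain why rules that can handle a baseline-only record should skip it, and it does not touch the conflict between 7.2 and 7.4.

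A reader might infer that under 7.4 an early stopper certainly has no Day 8 MADRS. The documents do not say so. Section 7.4 rules out further assessments only when consent is withdrawn, and SAP Table 2 accepts a MADRS on Days 2 to 11 as Week 1. A reader might also infer that every efficacy-type analysis shares the restriction, but SAP 5.5.1.2 puts the well-being questionnaire (SAWB) on the safety set.

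**Conclusion.** The point holds in a limited form. The response, remission, copy-reference and tipping-point analyses leave out dosed participants with no post-baseline MADRS. The primary MMRM and all formal decisions are unaffected, so the tempting conclusion that the trial's main result is biased or its robustness claim false is not supported.

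Under assumed balanced early exits of 2% to 8% per arm, the response difference changes by less than 1 point and the copy-reference estimate by about 0.1 to 0.3 points. The tipping point is usually, though not always, somewhat lower on the wider set. Larger response shifts need an imbalance between arms, which the documents neither predict nor exclude. These figures rest on assumed exit timing, visit-level effects, correlations and response rates.

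The contradiction between Protocol 7.2 and 7.4 is textual and needs no assumption. Its effect on the FAS is confined to the few who stop before their first post-baseline MADRS.

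**What to change.** 1. In the SAP, run the missing-as-non-responder and missing-as-non-remitter analyses on all randomised, dosed participants with a baseline MADRS. Keep copy-reference and tipping point on the FAS and add the same runs on this wider set as supplementary, so that a change of population can be told apart from a change of assumption. Report by arm the number with a baseline but no post-baseline MADRS; Safety minus FAS nearly gives this, once anyone without a baseline MADRS is separated out. Cost: SAP wording, a few extra runs on existing data, and figures that will usually be slightly less favourable.
2. Reconcile Protocol 7.2 with 7.4 on assessments after study drug stops, and state in the SAP whether a MADRS taken after discontinuation counts towards FAS membership. Which conduct rule applies is for the sponsor to settle. Cost: wording only.
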